5.2.3 Withdrawal/Discontinuation from the Study

Participants are free to withdraw from participation in the study at any time upon request, without prejudice to further treatment the participant may need to receive. The investigator will request that the study participant complete all study procedures pending at the time of withdrawal.

A participant will be recorded as a screen failure for the study if any of the following occur **prior to** first administration of study vaccine:

- Eligibility criteria are not met.
- The participant requests to discontinue study participation.

If, after randomization, a participant withdraws from the study, an EOS eCRF will be completed and information related to the withdrawal will be documented in the eCRF. The investigator will document whether the decision to withdraw a participant from the study was made by the participant or by the investigator, as well as which of the following possible reasons was responsible for withdrawal:

- Lost to follow-up
- Death
- Study terminated by Sponsor
- AE or SAE (specify)
- Participant request (specify)
- Protocol deviation (specify)
- Physician/Investigator decision (specify)
- Pregnancy
- Other (specify)

The investigator must capture the reason for withdrawal from the study in the eCRF for all participants that withdraw.

If, after enrollment, a participant desires to withdraw from the study because of an AE, the investigator will try to obtain agreement to follow-up with the participant until the event is considered resolved or stable and will then complete the EOS eCRF.

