If a participant approaches the site requesting to receive off-study COVID-19 vaccine, the participant should be counseled and reminded of the Switchover study design (for Phase 1, 2, 3a and 3b cohorts) or the comparison with another active vaccine (for Cohort 3c) whereby all participants will receive active investigational vaccine. The participant should be encouraged to demonstrate evidence of a scheduled appointment to receive off-study COVID-19 vaccine. If, after counseling and confirmation of the appointment, a study participant maintains his/her interest in receiving off-study vaccine, he/she will be advised to preferably schedule off-study vaccine at least 28 days after last dose of study vaccine, the participant will not be eligible to receive Switchover/Further Study Vaccine vaccine (if the Switchover/Further Study Vaccine day has not passed) and the participant is asked to continue study procedures through Final Visit (Day 394).

If a participant withdraws from the study, he/she may request destruction of any remaining samples taken and not tested, and the investigator must document any such requests in the site study records and notify the Sponsor or CRO accordingly.

If a participant withdraws consent and specifies no further contact with him/her or persons previously authorized by the participant to provide this information, this should be documented by the investigator in the study source documents. If vital status (whether the participant is alive or dead) is being measured, publicly available information should be used to determine vital status only as appropriately directed in accordance with local law.

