5.3 Lost to Follow-Up

A participant will be considered lost to follow-up if he or she fails to return for scheduled visits or is unable to be contacted by the study site.

The following actions must be taken if a participant fails to return to the clinic for a required study visit:

- The site must attempt to contact the participant and reschedule the missed visit as soon as possible and counsel the participant on the importance of maintaining the assigned visit schedule and ascertain whether the participant wishes to and/or should continue in the study.
- Before a participant is deemed lost to follow-up, the investigator or designee must make every effort to regain contact with the participant (where possible, 3 telephone calls and, if necessary, a certified letter to the participant's last known mailing address or local equivalent methods). These contact attempts should be documented in the participant's medical record.

If the participant continues to be unreachable, he/she will be considered to have withdrawn from the study at the date of last study contact.

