8.5.3 Sample Size for Phase 3c Substudy

Immunogenicity endpoints will be evaluated in participants in the Phase 3c-1 IAS (Section 8.2). Sensitivity analyses will be performed in the Phase 3c PP set. For the primary immunogenicity noninferiority endpoint of neutralizing antibody (using the pseudovirus microneutralization assay [MNT]) geometric mean ratio (GMR), assuming a GMR of ≥ 0.9 and a coefficient of variation of variation of 4.6, a sample size of 800 participants in Phase 3c-1 will provide greater than 90% power to exclude a non-inferiority boundary of 0.67 based on the use of a one-sided test at the alpha=0.025 level of significance, accounting for a dropout rate of approximately 20-25% due to the national COVID-19 vaccination campaign in Vietnam.

The primary safety endpoints of Phase 3c will be conducted in the Phase 3c Safety Analysis Set and Phase 3c Reactogenicity Analysis Set (Section 8.2). With a sample size of approximately 2,400 participants randomized and with approximately 1,200 participants randomized in the study to receive ARCT-154 or ChAdOx1 for the safety analysis, based upon the following formula, if the incidence rate of an adverse event is 0.1%, the probability to detect one event in 1,200 vaccinated participants is 69.9% and if the incidence rate is 1.0% the probability is more than 99%:

$$p = 1 - (1 - R)^N$$

where R = incidence rate and N = sample size

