#### Sample Size for Phase 3b

The primary safety endpoints will be evaluated in the Phase 3b SAS and the Phase 3b RAS. With a sample size of ~16,000 participants randomized and with approximately 8,000 participants randomized in the study to receive ARCT-154 for the primary safety analysis, if the incidence rate of an adverse event is 0.1%, the probability to detect one event in 8,000 vaccinated participants is >99.9%, based upon the following formula:

$$p = 1 - (1 - R)^N$$

where R = incidence rate and N = sample size

For the overall primary efficacy objective of the study, the null hypothesis is that the vaccine efficacy (VE) of ARCT-154 to prevent first occurrence of polymerase chain reaction (PCR)-confirmed COVID-19 is  $\leq 30\%$  (ie,  $H_0^{\text{efficacy}}$ : VE  $\leq 0.3$ ).

The primary efficacy objective will be met if the lower limit of the 95% CI for VE exceeds 30%.

VE is defined as the percent reduction in the hazard of the primary endpoint (ARCT-154 versus placebo). Equivalently, the null hypothesis is as follows:

- $H_0^{\text{efficacy}}$ : HR > 0.7 (equivalently, proportional hazards VE  $\leq 0.3$ )

A Cox proportional hazard model will be used to assess the magnitude of the study group difference (ie, HR) between ARCT-154 and placebo at a 1-sided 0.025 significance level.

Under the assumption of proportional hazards over time and with 1:1 randomization of ARCT-154 and placebo, a total of 372 COVID-19 cases will provide approximately 90% power to detect a 50% reduction in hazard rate (50% VE), rejecting the null hypothesis with a 1-sided false positive error rate of 0.025.

The study will be considered positive at the primary analysis if the one-sided p-value for rejecting HR  $\geq 0.7$  is less than or equal to 0.025.

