### Phase 3b Statistical Hypothesis

The overall primary endpoints for the study are evaluated in the Phase 3b population as follows:

- The overall primary efficacy endpoint for the study is vaccine efficacy as evaluated in the Phase 3b Modified Intent to Treat (mITT) population
- The overall primary safety endpoints are those evaluated in the Phase 3b Safety Analysis Set (SAS) and Phase 3b Reactogenicity Analysis Set (RAS)

There is no hypothesis testing for safety data analysis. Where statistical methods are applied, the emphasis will be on estimation with 95% CIs.

The primary statistical analyses for VE will be performed using virologically confirmed COVID-19 cases as adjudicated in a blinded fashion by the Independent Adjudication Committee.

The null hypothesis ( $H_0^{\text{Efficacy}}$ ) as follows:  $H_0^{\text{Efficacy}}: \text{VE} \leq 30\%$

VE is estimated as 1-HR, where HR is the hazard ratio, and will be presented together with 95% CIs. The primary efficacy objective will be met if the lower limit of the 95% CI for VE exceeds 30% in the Phase 3b mITT population.

Under the assumptions of proportional hazards over time and a 50% reduction in hazard rate (50% VE) and with 1:1 randomization of ARCT-154 and placebo, a total of 372 confirmed COVID-19 cases will provide approximately 90% power to reject the null hypothesis ( $H_0: \text{VE} \leq 30\%$ ), using a log-rank test statistic with a 1-sided false positive error rate of 0.025.

The secondary efficacy objectives (and second primary objective for regulatory filings outside of Vietnam) will be met if the lower limit of the 95% CI for VE exceeds 0%.

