Exploratory 4b	COVID-19 with onset at any time after the first dose of study vaccine administration and up to Day 92	ITT + no prior infection (3b & Pooled)	[Last date at risk – Date received 1st dose]+1	No
Exploratory 5a	Severe COVID-19 with onset between Day 36 and Day 92 by specific variant	miITT (3b & Pooled)	[Last date at risk – Date received 1st dose]+1	No
Exploratory 5b	Severe COVID-19 with onset at any time after the first dose of study vaccine administration and up to Day 92	ITT + no prior infection (3b & Pooled)	[Last date at risk – Date received 1st dose]+1	No

\*COVID-19 events will be confirmed, protocol-defined cases. \*\* Where the last date at risk will be defined as COVID-19-event date or censor date, whichever comes first.

(a) Unless specified otherwise, reference to the protocol endpoints is a reference to the Phase 3b endpoints.

Confirmed, protocol-defined COVID-19 cases will be determined by case report form (CRF) data, as confirmed by the blinded Independent Adjudication Committee and adjudicated for severity, with the date of case onset as date of symptom onset and date of positive COVID test date, whichever occurs first. Both protocol-defined and (protocol-defined) severe cases flagged in the CRF will be included in the primary endpoint.

For participants with no covid-event during the time interval the censor date for the last date at risk is whichever of the following comes first:

- Date of completion of Day 92 visit;
- Date of death unrelated to COVID-19;
- Date of receipt of Switchover or receipt of non-study COVID-19 vaccine
- Lost to Follow-up (last known alive date or date of Day 1+91 days, which is earlier).

Section 9.2.2 presents the endpoints and analyses in terms of estimands for primary, secondary and exploratory efficacy analyses.

As a sensitivity analysis of the primary endpoint (Phase 3b only), severe cases and deaths due to COVID-19 will be repeated using all COVID-19 cases from CRF, including those cases that are not confirmed by the blinded Independent Adjudication Committee and with severe or death severity as reported in the CRF.

Day 36 is defined as second dose+7 days (29+7=36 days), and Day 92 is defined as second dose+63 days (29+63=92 days). Another sensitivity analysis of the primary endpoint (Phase 3b only) will be performed using Day 92 visit instead of second dose+63 days.

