Section 8.7.2 Table 18 estimand 2 (efficacy)	Imputation/Data/Censoring Rules: For deaths unrelated to COVID-19, censor at date of death. For participants who undergo Switchover/Further Study Vaccine or receive a non-study COVID-19 vaccine, censor at date of Switchover or non-study vaccination.	Participants last date at risk date will also be censored for Lost to Follow-up	Add rule of handing censoring condition for lost to follow-up scenario.
Section 8.7.2 Table 18 estimand 2 (efficacy)	Sensitivity: the same analysis will be performed in the Pooled mITT and Phase 3b PP analysis sets.	
2 additional sensitivity analyses to be performed.
 
 
• A sensitivity analysis of all Covid cases reported in CRF and not confirmed by the blinded Independent Adjudication Committee or with severity as reported in the CRF has been added for the primary endpoint, severe cases and deaths due to COVID-19.
 
• Day 36 is defined as second dose+7 days (29+7=36 days), and Day 92 is defined as second dose+63 days (29+63=92 days). Another sensitivity analysis of the primary endpoint (Phase 3b only) will be performed using Day 92 visit instead of second dose+63 days.
 
	Add additional sensitivity analyses to assess the robustness of the primary analysis results.
Section 8.7.2 Table 18 estimand 3 (safety)	Supportive: Analysis will be performed for different time intervals, specifically:	As per section 6.6.1.3 of this SAP, only the following intervals will be done:	To summarize study periods that are not overlapping

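### SAP 6.4 gives no censoring date for event-free participants who withdraw, and dates those lost to follow-up by last known alive, not by last study contact

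*SAP*

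**What the plan says.** SAP 6.4 (text after Table 6) defines the last date at risk as the event date or the censor date, whichever comes first. Participants without an event are censored at the earliest of four dates:

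1. completion of the Day 92 visit;
2. death unrelated to COVID-19;
3. Switchover or receipt of a non-study COVID-19 vaccine;
4. "Lost to Follow-up (last known alive date or date of Day 1+91 days, which is earlier").

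SAP 7.1 records the fourth item as a change from the protocol: "Participants last date at risk date will also be censored for Lost to Follow-up". The censoring column for Estimand 2 in Protocol Table 18 mentions unrelated death, Switchover and non-study vaccine, but not withdrawal.

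Protocol 5.2.3 lists nine reasons for leaving the study. Lost to follow-up is one, and "Participant request (specify") is another. The rest are death, sponsor termination, adverse event, protocol deviation, investigator decision, pregnancy and other. For a participant who stays unreachable, Protocol 5.3 says that "he/she will be considered to have withdrawn from the study at the date of last study contact".

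Nothing else supplies a date. SAP 5.4 has withdrawals and dropouts in its title but deals only with replacement, and SAP 6.2.6 says that missing data are not imputed. The safety estimand in SAP 9.2.3 does name early withdrawal as an end of observation, so the omission is specific to efficacy.

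**The concern.** Of the nine exit reasons, death and loss to follow-up have a rule, which leaves seven without one. Take a participant who withdraws by request on Day 60, event-free, with no Day 92 visit and no recorded outside vaccine. None of the four dates exists, so time at risk cannot be computed. A participant who had COVID-19 on Day 45 and then withdrew on Day 60 has an event date and a valid time. If records without a time are discarded, being retained depends on the outcome.

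The rule for those who are lost has a different problem. COVID-19 cases are found through visits and calls at which symptoms are reviewed. A date on which someone was merely known to be alive may fall after the last such contact, so event-free time is credited when no case could have been detected. The first problem removes valid person-time and the second adds unobserved person-time.

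The same list serves the primary endpoint and both key secondary endpoints (severe COVID-19, and COVID-19 at any time after the first dose).

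**Working it through.** **The plan's own figure.** SAP 6.2.3 sizes Phase 3b "using a log-rank test statistic with a 1-sided false positive error rate of 0.025", with null HR 0.7, assumed HR 0.5, 1:1 allocation and about 90% power.

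Events = 4(z₀.₉₇₅ + z₀.₉₀)² / [ln(0.5/0.7)]² = 4(1.960 + 1.282)² / (0.3365)² ≈ 371.2, rounded up to 372. Power at 372 events is 0.9006. The planned event count is reproduced and does not depend on the censoring rule.

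**Inputs for the effect of deletion.** From the documents: 8,000 per arm (Protocol 4.1), a window from Day 36 to Day 92 inclusive (92 − 36 + 1 = 57 days), true VE 50%, and 372 events when nobody withdraws. Assumed: constant hazards, withdrawal times uniform over the window, and withdrawal of 5% to 25% per arm. The documents give no Phase 3b withdrawal rate. Protocol 8.5.3 gives a dropout figure for Phase 3c only ("accounting for a dropout rate of approximately 20-25% due to the national COVID-19 vaccination campaign in Vietnam").

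**Formula.** Let a fraction w of an arm withdraw. Events are rare (placebo risk about 3.1% over the window), so events are close to proportional to 1 − w/2. Person-time is proportional to 1 − w/2 if withdrawn non-cases are censored at withdrawal, and to about 1 − w if they are deleted. Deletion therefore multiplies an arm's rate by about f(w) = (1 − w/2)/(1 − w), and

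HR after deletion ≈ 0.5 × f(w vaccine) / f(w placebo).

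Example, vaccine 10% and placebo 20%: f = 0.95/0.90 = 1.056 and 0.90/0.80 = 1.125, so HR ≈ 0.5 × 0.938 = 0.469 and VE ≈ 53.1%.

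**Results, exact under the same assumptions:**

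| Withdrawal, vaccine / placebo | VE, censored | VE, deleted |
|---|---|---|
| 5% / 5% | 50.0% | 50.0% |
| 25% / 25% | 50.0% | 50.0% |
| 5% / 10% | 50.0% | 51.4% |
| 10% / 5% | 50.0% | 48.6% |
| 10% / 20% | 50.0% | 53.1% |
| 20% / 10% | 50.0% | 46.7% |
| 15% / 25% | 50.0% | 53.3% |
| 25% / 15% | 50.0% | 46.4% |

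Simulated Cox fits (10 trials per scenario) agree: shifts of −0.1, +3.3 and −3.3 points at 10/10, 10/20 and 20/10%.

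With balanced withdrawal VE is stable, but deletion still inflates each arm's rate per person-time by f(w): 1.026, 1.056, 1.125 and 1.167 at 5, 10, 20 and 25%. SAP 6.4.1 reports surveillance time and case proportions by arm, so those tables would be affected even if VE were not.

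The effect of last known alive versus last contact cannot be sized, because the documents give no distribution for the gap between the two dates.

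**The case against.** The strongest reply is that the SAP never says withdrawn non-cases are removed. Its lead-in assigns a censor date to everyone without an event. Protocol 5.3 opens by treating a participant who fails to return for scheduled visits as lost to follow-up, so someone who leaves on Day 60 and misses Day 92 could be censored under the fourth item. That stands: deletion is an inference from the closed list, the no-imputation rule and an example PROC PHREG call that needs a non-missing time. But this reading merges categories that Protocol 5.2.3 keeps apart, and it sends withdrawals to the last-known-alive date.

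Second, people who leave for a licensed vaccine are already censored under the third item when the date is known, and they are asked to stay in the study. This also stands, within limits. Protocol 4.4 foresees participants leaving to pursue vaccination elsewhere, and Protocol 6.8.1 records outside vaccines only while participation lasts, so a vaccination after exit may have no date.

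Third, a reader might infer that lost participants are credited with time from public records, because Protocol 5.2.3 says "publicly available information should be used to determine vital status". The documents do not support that. The sentence concerns people who withdraw consent and refuse contact, and it is conditional on vital status being measured. For Phase 3b, weekly calls run to Day 85 and the SAP date is capped at Day 1+91, so the excess time is bounded.

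Fourth, the primary conclusion looks robust at the design value. With 124 and 248 cases, SE(ln HR) = √(1/124 + 1/248) = 0.110, so VE 50% has a lower limit of 1 − 0.5 × e^(1.96 × 0.110) = 38.0%. At the worst tabulated value, 46.4%, the limit is 1 − 0.536 × 1.241 = 33.5%. Scaling the SE to that scenario's 338 events (0.110 × √(372/338) = 0.115) gives about 32.8%. Both exceed the 30% bound. This limits the severity but does not supply the missing rule.

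**Conclusion.** The gap is confirmed: no passage dates the end of risk for an event-free participant who withdraws for a reason other than loss to follow-up. So is the conflict between last known alive (SAP 6.4) and last study contact (Protocol 5.3).

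The consequence is conditional. If the list were applied literally and records without a time were discarded, VE would be essentially unchanged with equal withdrawal by arm. It would shift by about 1.4 to 3.6 points under an assumed 5 to 10 point difference, upward if placebo withdrawal is higher and downward if vaccine withdrawal is higher.

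A reader might infer that the plan does delete these participants, or that the primary VE is biased upward. The documents support neither. Deletion is not stated, the direction depends on which arm loses more people, and the size rests on withdrawal rates that the documents do not give for Phase 3b. The Phase 3c dropout figure cannot stand in for them.

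The rule should still be settled in text. It governs the primary endpoint, the two available readings err in opposite directions, and SAP 2.4 says that some authors of this SAP had participant-level unblinded data.

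**What to change.** Replace the fourth censoring item in SAP 6.4 with:

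*Withdrawal from study for any reason, or loss to follow-up: date of last study contact at which COVID-19 symptoms were reviewed (visit or call), not later than Day 92.*

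Apply it to the COVID-19 and severe COVID-19 endpoints. Keep last known alive only for the COVID-19 death endpoint, where vital status is what is being followed. This also brings the SAP into line with Protocol 5.3.

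SAP 2.5 describes unblinded efficacy analyses on a 30 March 2022 cut, so the change must be visible as one made after unblinding. Enter it in SAP Section 7, state how the earlier analyses treated withdrawals, and report by arm how many participants are affected. SAP Parts 1 and 2 are not among the documents reviewed. SAP 7.1 presents loss-to-follow-up censoring as a change that they did not introduce, so their actual handling needs to be stated.

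The cost is one sentence of SAP text, a programming change and a short count table. The documents do not show that the dates of symptom-review calls are held in the EDC system, so the sponsor should confirm this before the rule is finalised.

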#### 6.4.1 Primary Efficacy Analysis

The analysis of the first primary endpoint will consider the first occurrence of confirmed, protocol-defined COVID-19 with onset between Day 36 and Day 92 inclusive.

Time at risk = [Last date at risk – (Date received 2nd dose + 7 days)]+1; where the last date at risk will be defined as COVID-19-event date or censor date, whichever comes first.

Summaries of vaccine efficacy will display the number of participants included in the analysis, number of protocol-defined COVID-19 cases (Protocol Appendix 2) and surveillance time in person-year will be summarized in each vaccine group. Surveillance time refers to the total person-time at risk (years) for the given endpoint.

The vaccine efficacy (VE) is defined as the percent reduction in the hazard rate of the COVID-19 events (ARCT-154 versus placebo). The vaccine efficacy is calculated as:

$$VE = 1 - \frac{h_{ARCT-154}}{h_{placebo}} = 1 - HR$$

where  $h_{ARCT-154}$  and  $h_{placebo}$  are hazard rates of the confirmed, protocol-defined COVID-19/Severe COVID-19/death among those in ARCT-154 group and placebo group, respectively.

Vaccine efficacy will be displayed together with 95% confidence interval (CI). Vaccine efficacy is calculated from 1-hazard ratio, where, the hazard ratio (HR) and 95% CI are measured by adjusted Cox proportional hazard regression, with the assumptions of proportional hazards over time. The p-value will be calculated from Cox proportional hazard regression.

Efficacy summaries will also include the proportion of participants with COVID-19 cases in each vaccine group will be displayed together with the Clopper-Pearson 95% CI and a comparison between ARCT-154 and Placebo with 95% CIs. A Log-Rank test p-value will be calculated (in addition to VE% Cox model p-value).

Factors to be used as covariates in Cox proportional hazard regression include:

- Risk group: A randomization stratification factor for age and health risk for severe disease;  $\geq 18$  to  $< 60$  years and “healthy”,  $\geq 18$  and  $< 60$  years and “at risk” and  $\geq 60$  years. Age and health risk at randomization collected in the CRF will be used.
- Study site region: Study site is a randomization stratification factor. However, the sites are grouped into study site region for adjustment factor. Site collected in the CRF will be used.
  - Risk group or study site region will be removed from the model when performing subgroup analysis on that variable.

A Kaplan-Meier plot will be provided for the primary endpoint.

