8.7.5 Analysis of Pooled Efficacy and Safety Endpoints

The pooled safety primary endpoints include the number of participants (%) with solicited AEs, unsolicited AEs, MAAEs, SAEs, and AEs leading to discontinuation/withdrawal and will be evaluated in the Pooled SAS and the Pooled RAS.

The pooled efficacy primary endpoint is the incidence rate of virologically confirmed COVID-19. This analysis will be conducted as a sensitivity analysis to the Phase 3b primary endpoint for the study and will be carried out in the Pooled mITT.

The analysis will be conducted using the same methods as described for the Phase 3b primary efficacy analysis (Section 8.7.3.4) and Phase 3b primary safety analysis (Section 8.7.3.2).

Definition and handling of intercurrent events is described in Section 8.3.1.

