## 2.2 Randomization Methodology

Phase 1, 2 and 3a participants were randomly assigned 3:1 (ARCT-154:placebo), while Phase 3b participants were randomly assigned 1:1 (ARCT-154:placebo).

- Participants in Phase 1 and 3b received two doses of one type of study vaccine on Day 1 and 29 (ARCT 154 or placebo) and then two doses of the opposite vaccine (placebo or ARCT-154) on Day 92 and 120 (referred to as ‘Switchover’).
- Participants in Phase 2/3a who received ARCT-154 in the initial two-dose vaccination series were further randomized via IVRS to receive either ARCT-154 or placebo (in a 3:1 ratio) at Day 92 followed by placebo at Day 120 (referred to as “Re-randomization”). Participants that received placebo in the initial vaccination series underwent Switchover to receive ARCT-154 at Day 92 and Day 120 (referred to as “Switchover”).

Phase 3c participants were randomized 1:1 to receive ARCT-154 or ChAdOx1; no Switchover or re-randomization occurred for Phase 3c participants as all participants in this cohort receive active vaccine.

For Phases 2, 3a, 3b and 3c, prior to randomization, participants were stratified by the following 3 stratification factors:

- Age < 60 at high risk of severe COVID-19
- Age < 60 not at high risk of severe COVID-19
- Age ≥ 60 years of age (considered at risk of severe COVID-19 by default)

Participants were defined as “at risk” if they are 60 years of age or older OR have medical history described as putting an individual at risk or possibly at risk of severe coronavirus disease 2019 (COVID 19).

As the eligibility criteria for Phase 1 exclude participants ≥ 60 years of age or otherwise at risk for severe COVID-19, stratification did not occur for Phase 1.

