## 4 ANALYSIS SETS

### 4.1 Analysis Set Definitions

- **All Screened Participants:** Includes all participants who signed informed consent form. This analysis sets are defined for each Phase of the study as follows:
  - Phase 1/2/3a: this pools data from Phase 1, 2 and 3a participants
  - Phase 3b
  - Phase 3c
  - Pooled: this pools data from Phase 1, 2, 3a and 3b participants
- **Randomized Set (RS):** Includes all participants who are randomly assigned in the study regardless of the participants' vaccination status in the study. Participants will be analyzed according to the vaccine to which the participant was randomly assigned. RS are defined for each Phase of the study as follows:
  - Phase 1/2/3a RS: this pools data from Phase 1, 2 and 3a participants
  - Phase 1 RS
  - Phase 2/3a RS
  - Phase 3b RS
  - Phase 3c RS
  - Pooled RS: this pools data from Phase 1, 2, 3a and 3b participants

Participants who are entered into the unblinded part of IVRS will receive a random ID (randomID). Participants who received a randomID will be entered into the blinded part of the IVRS to receive the treatment assignment. Participants with an assigned randomID but without assigned treatment in the IVRS system will not be considered as randomized.

- **Intent-to-Treat (ITT) Analysis Set:** Includes all participants who receive any dose of study vaccine (ARCT-154 or placebo or ChAdOx1). Participants will be analyzed according to the vaccine to which the participant was randomly assigned. ITT are defined for each Phase of the study as follows:
  - Phase 3b ITT
  - Phase 3c ITT
  - Phase 1/2/3a ITT: this pools data from Phase 1, 2 and 3a participants and will include evaluations up to Day 92 only
  - Pooled ITT: this pools data from Phases 1/2/3a/3b and will include evaluations up to Day 92 only

- **Modified Intent-to-Treat (mITT) Analysis Set:** Includes all participants who received all protocol-required doses of study vaccine (ARCT-154 or placebo or ChAdOx1) up to the evaluation timepoint concerned, and who have no evidence of SARS-CoV-2 infection (no positive RT-PCR or other COVID-19 test or seropositivity for anti-nucleocapsid antibody) on Day 1 or up to 7 days after the 2nd study vaccination. The mITT analysis set will be analyzed according to vaccine assigned. The mITT analysis sets are defined for:
  - Phase 3b mITT
  - Phase 1/2/3a mITT
  - Phase 3c mITT
  - Pooled mITT: this pools data from Phases 1/2/3a/3b and will include evaluations up to Day 92 only

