## 9.5 Example SAS code

### Time to Event/Hazard Ratio used for VE%:

```
proc phreg data=;
  class Treatment(ref='Placebo') Risk_group site_region;
  model aval*cnsr(1) = Treatment Risk_group site_region;
  estimate 'HR' Treatment 1 /exp cl;
  ods output estimates=est;
run;
```

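### Pooled efficacy analyses mix parts randomised 3:1 and 1:1 with no term for part, so pooled VE can shift if background hazard differs between parts (minor; nominal analyses only)

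*SAP*

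**What the plan says.** Allocation differs by part. SAP 2.2 states: "Phase 1, 2 and 3a participants were randomly assigned 3:1 (ARCT-154:placebo), while Phase 3b participants were randomly assigned 1:1 (ARCT-154:placebo". SAP 4.1 then merges the parts: "Pooled mITT: this pools data from Phases 1/2/3a/3b and will include evaluations up to Day 92 only". Protocol 8.7.5 carries the method across: "The analysis will be conducted using the same methods as described for the Phase 3b primary efficacy analysis".

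That method is in SAP 6.4.1. After "Factors to be used as covariates in Cox proportional hazard regression include" come two items, risk group and study site region. The example code in SAP 9.5 agrees: "model aval*cnsr(1) = Treatment Risk_group site_region", with no phase term and no STRATA statement. SAP 6.4.1 also says "A Log-Rank test p-value will be calculated (in addition to VE% Cox model p-value", with no stratification stated. It asks for "a comparison between ARCT-154 and Placebo with 95% CIs", without naming the measure, and adds "A Kaplan-Meier plot will be provided for the primary endpoint". No section adds part or calendar time.

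Protocol 8.4.4 calls pooled statistics nominal, and SAP 6.2.4 treats all pooled endpoints as sensitivity analyses to Phase 3b.

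**The concern.** ARCT-154 is 75% of Phase 1/2/3a and 50% of Phase 3b, so in the pooled set part is associated with treatment. Randomisation protects the comparison within each part, but not in an unstratified pool. Any difference in background hazard between parts that risk group and region do not capture then enters the treatment effect.

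Such a difference is plausible but not shown. Phase 3b opens only after Phases 2 and 3a have finished enrolling (Protocol 4.4). The Amendment 8 rationale describes national incidence falling and later rising. SAP 7.2 cites differing background risk among sites as its reason for adding region as a subgroup.

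What is at stake is interpretation. Pooled VE exists to be read against Phase 3b VE, and a gap caused only by mixing allocation ratios could be taken as support or contradiction. For most endpoints a separate Phase 1/2/3a estimate helps the reader see what happened. There is none for the pooled PP analyses, for the by-variant endpoints (Exploratory 4 and 5 in Table 6), or for the pooled analyses of all CRF-reported cases in SAP 6.4.1.1. For Exploratory 1 to 3 the SAP is inconsistent: 6.4.3 lists Phase 3b and Pooled only, while Table 6 adds Phase 1/2/3a.

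**Working it through.** **1. The plan's own figure.** The documents give no figure for the pooled analysis. The Phase 3b event count (SAP 6.1) reproduces. With HR 0.7 under the null, 0.5 under the alternative, 1:1 allocation, one-sided 0.025 and 90% power, the Schoenfeld formula gives 4 × (1.960 + 1.282)² / [ln(0.5/0.7)]² = 371.2, so 372 events and 90.06% power.

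**2. Imbalance by design.** Phase 1/2/3a supplies 750/8,750 = 8.6% of the pooled ARCT-154 arm and 250/8,250 = 3.0% of the pooled placebo arm (Protocol 4.1).

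**3. Crude pooled VE.** Let r be the Phase 1/2/3a background hazard divided by that of Phase 3b (assumed). With rare events and the same true HR of 0.5 in both parts:

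pooled HR = 0.5 × [(8,000 + 750r)/8,750] / [(8,000 + 250r)/8,250]

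- r = 0.5: 0.5 × (8,375/8,750)/(8,125/8,250) = 0.486, VE 51.4%
- r = 2: 0.5 × (9,500/8,750)/(8,500/8,250) = 0.527, VE 47.3%
- r = 3: 0.5 × (10,250/8,750)/(8,750/8,250) = 0.552, VE 44.8%

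At r = 1 it is 50.0%. With no vaccine effect, the same ratio gives pooled VE of +2.8%, -5.4% and -10.4% at r = 0.5, 2 and 3.

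**4. Does region stand in for part?** Only partly. The site table in SAP 6.2.5 codes phase in the first digit of the site ID. Phase 3b has 1 site in North HMU, 6 in South PasteurHCM and 8 in North VMMU. Phase 1/2/3a has site IDs in HMU (101, 201, 202, 302) and South (203, 303) and none in VMMU. I took the large-sample limit of a model with treatment and region, splitting Phase 3b 1:6:8 over HMU:South:VMMU (assumed equal-sized sites). The HMU share of Phase 1/2/3a ran from 0.1 (the only Phase 1 site is in HMU, 100/1,000) to just under 1.

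| Pooled VE at true VE 50% | r = 0.5 | r = 2 | r = 3 |
|---|---|---|---|
| No adjustment | 51.4% | 47.3% | 44.8% |
| Region term, equal regional hazards (assumed) | 50.8-51.3% | 47.5-48.4% | 45.1-47.0% |
| Region term, regional hazards 1.5:1:0.5 or 0.5:1:1.5 (assumed) | about 50.4-51.9% | about 46.5-49.3% | about 43.2-48.6% |
| Stratified by part | 50.0% | 50.0% | 50.0% |

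The second and third rows are examples, not bounds. With hazards 1.5:1:0.5 the region-adjusted shift exceeds the crude shift in the first row, which takes regional hazards as equal.

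**5. Scale.** With 372 events at VE 50% (124 and 248 by arm), the standard error of the log HR is √(1/124 + 1/248) = 0.110. The 95% CI for VE is 38.0% to 59.7%.

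**6. Price of stratifying.** Compare d1·d0/(d1 + d0) summed over parts with the same quantity for the pool, where d1 and d0 are expected cases by arm. The information ratios are 0.992, 0.985, 0.974 and 0.964 at r = 0.5, 1, 2 and 3. The standard error therefore rises by 0.4%, 0.7%, 1.3% and 1.8%.

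**7. Proportions, if compared as a risk difference.** Assume placebo risk 3.1% in Phase 3b (248/8,000). At r = 3 the crude pooled difference is -1.47 points, outside both parts (-1.55 and -4.65). A Mantel-Haenszel difference with weights 4,000 and 187.5 is -1.69.

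**The case against.** The strongest reply is that nothing turns on this. The confirmatory test is in the Phase 3b mITT, which is 1:1 throughout. Pooled statistics are nominal, and for the primary endpoint SAP 6.4 and Table 6 give Phase 3b, Phase 1/2/3a and Pooled results separately. The illustrated shifts lie inside the sampling error in step 5. All of that stands, and it keeps the point minor.

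Second, the bias is conditional. At r = 1 within risk group and region the adjusted Cox model is unbiased. Phase 3b may open after the Phase 2/3a Day 8 review, so follow-up may overlap. The Amendment 8 account of incidence is national, not by part. This also stands: the documents do not establish any r other than 1.

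Third, a change now is post hoc. SAP 2.5 keeps the efficacy data cut at 30 March 2022, SAP 2.1 says methods will be consistent with the earlier SAPs, and SAP 2.4 records that some authors had unblinded access. This bears on how the change is reported, not on whether the model is better.

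A reader might infer more than the documents support. One inference is that the primary VE is contaminated; it is not, because it uses Phase 3b alone. Another comes from Protocol 8.1, whose hierarchy refers to pooled secondary endpoints and so might make them confirmatory. But that section names the Phase 3b endpoints as key secondaries and the pooled ones as sensitivity analyses, and SAP 6.2.4 drops the word pooled from the hierarchy.

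**Conclusion.** The point holds as a minor one. The pooled efficacy analyses join parts with different allocation ratios and carry no term for part. Pooled VE can therefore shift for a reason unrelated to vaccine effect, and region adjustment does not reliably remove it. At a true VE of 50% the illustrated shifts run from under 1 point to about 7 points for r between 0.5 and 3.

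These sizes rest on assumed r, planned sample sizes, an assumed regional split of Phase 3b, assumed regional hazards and equal true VE in both parts. The documents supply no incidence by part, so it cannot be said that pooled VE is biased, or in which direction. Stratifying removes this one source of shift only. If VE in Phase 1/2/3a were 30% or 70%, the stratified pooled VE at r = 1 would be 48.9% or 51.1%, so it can still differ from Phase 3b. The Phase 3b primary analysis and the separate Phase 1/2/3a analyses are unaffected, because each has a single allocation ratio.

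**What to change.** For the pooled efficacy analyses only, amend SAP 6.4.1 and 9.5 to stratify the Cox model and the log-rank test by part, with two levels (Phase 1/2/3a and Phase 3b), for example `strata phase;` in the pooled PHREG call. Record the change in SAP section 7 as made after unblinded analyses, and show the unstratified estimate beside the stratified one. Leave the Phase 3b analysis unchanged.

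Two additions are optional. If the comparison of proportions is a risk difference, use a part-stratified Mantel-Haenszel difference with its 95% CI. Label the pooled Kaplan-Meier curves as unadjusted for part.

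The cost is one code statement, a sentence in 6.4.1, a row in section 7, one extra estimate per pooled efficacy table, and the small loss of precision in step 6. No new data are needed.
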